## Secondary Objectives

- **Explore the differences in demographic and clinical characteristics among tofacitinb+MTX patients who discontinue MTX vs. persist with MTX or experience interrupted MTX.**

For this objective descriptive analysis will be conducted. The goal of this objective will be to describe the respective populations and explore the presence of demographic differences between the cohorts. Known demographic characteristics (eg, age, gender geographic location, pre-index cost and utilization) will be summarized. In addition, other patient characteristics (eg, most common comorbid diagnoses and most common medications received) will be summarized.

- **To compare RA-related costs among tofacitinb+MTX patients who discontinue MTX vs. persist with MTX or experience interrupted MTX.**

For this objective both descriptive and multivariable analysis will be conducted. For the descriptive analysis, 12-month RA-related cost measures will be presented per patient during the baseline and follow-up periods. The change in health care cost from baseline to follow-up will be identified. In addition, total RA-related health care cost will be presented in each of the months of the baseline and follow-up. The mean cost in each month will be included on a figure demonstrating the trend in costs over time. Multivariable analysis of cost will also be conducted using generalized linear models (see [Section 8.10.3](#)).

- **Compare medication effectiveness using a validated claims-based algorithm among tofacitinb+MTX patients who discontinue MTX vs. persist with MTX or experience interrupted MTX.**

Medication effectiveness at one year will be examined by the medication cohorts of interest using patients who have at least 1 year of follow-up. For this objective both descriptive analysis and multivariable analysis will be used. Descriptive analysis will focus on quantifying the percentage of patients who are effectively treated at one year. Analysis of this objective may also include multivariable analysis (eg, logistic regression). Specifically, the dependent variable will be effectively treated at one year (yes/no) and the independent variables will be study cohort, demographic characteristics, characteristics of interest, and other characteristics identified from previous objectives (see [Section 8.10.4](#)).

- **Compare all-cause and RA-related health care utilization among tofacitinb+MTX patients who discontinue MTX vs. persist with MTX or experience interrupted MTX.**

For this objective descriptive analysis will be conducted. Utilization measures (flags and 12-month counts) will be presented per patient during the baseline and follow-up periods. In addition, for counts the change from baseline to follow-up will be calculated.

- **Compare all-cause healthcare costs among tofacitinib+MTX patients who discontinue MTX vs. persist with MTX or experience interrupted MTX.**

For this objective descriptive and multivariable analysis will be conducted. For the descriptive analysis, 12-month cost measures will be presented per patient during the baseline and follow-up. The change in 12-month costs from the baseline to the follow-up will also be calculated. In addition, total all-cause cost will be presented in each of the months of the baseline and follow-up. The mean cost in each month will be included on a figure demonstrating the trend in costs over time. Multivariable analysis of follow-up health care cost will also be conducted using generalized linear models (see [Section 8.10.3](#)).

- **Evaluate the primary and secondary objectives in cohorts of interest.**

All objectives will be evaluated for Commercial and Medicare Supplemental lives separately as well as by Monotherapy vs. Combination regimens as identified in [Section 8.10.2](#) and by prior biologic experience (0, 1, 2, 3+ at any time prior to index).

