### 8.2.1. Inclusion Criteria

This study will include individuals who are privately insured and with Medicare Supplemental insurance paid for by their employers and initiating tofacitinib in combination with MTX for RA between 01 January 2014 and 31 January 2017. To be included in the final study sample, patients must meet the following inclusion criteria:

1. At least one claim for tofacitinib between 01 January 2014 and 31 January 2017 (the identification period).

- a. **Medication index date.** The index date will be the date of the first claim for tofacitinib during the identification period.

*Note: Patients will have a variable length baseline of at least a year long. The baseline period will be censored at January 1, 2012 based on licensed data availability. The majority of baseline measures will use data from the 12 months immediately prior to the index date. Select measures will use data during the entire variable length baseline.*

- b. Tofacitinib initiation. Patients must have a 2nd claim for tofacitinib within 60 days of the end of the days supplied from their index claim (at least two claims with no 60 day gap).
- c. Oral MTX initiation. Patients must have an initial prescription for oral MTX in the period between 30 days prior to index date and 30 days following index date followed by a 2nd prescription for oral MTX within 60 days of the end of the days supplied from their initial MTX claim (at least two claims/administrations with no 60 day gap).

2. Presence of The International Classification of Diseases, 9th Revision, Clinical Modification (ICD-9 CM) code for RA (in any position) during the one-year pre-index period or on the index date. ICD-9 = 714.0x-714.4x & 714.81 or ICD10 = M05.\* & M06.0\*-M06.3\* or M06.8\*-M06.9\*.

3. At least 18 years old as of the index date.

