### 8.4. Sample Subsets

The following sample subsets will be identified and included in the analysis of select outcomes.

- **Commercial vs. Medicare Supplemental-** Patients who meet all selection criteria and have Medicare Supplemental insurance at index will be classified as such.

- **Number of prior Biologics:** 0, 1, 2, 3+ at any time prior to index.
- **Pre-index MTX therapy:** Treatment with MTX prior to index medication.

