#### **8.10.2. Multivariate Analysis**

To control for possible confounding of the relationship between the outcomes and independent variable of interest, select objectives will be conducted utilizing multivariable methods as described above.

Final outcomes for multivariate analysis will be selected after review of descriptive results. Possible outcomes of interest include: total all-cause health care cost, total RA-related health care cost, cost of biologics/tofacitinib/administration/nb-DMARDs, medication effectiveness (yes vs. no).

For each model, specific predictors to be included will be determined based upon clinical rationale and statistical significance. Variables listed in [Section 8.6.1](#) and [8.6.2](#) will be considered for inclusion in the multivariable models. Additional variables identified throughout the course of the study will also be considered. Following standard procedure,

regression diagnostics will be performed for each model to assess goodness of fit and violations of model assumptions (eg, multicollinearity, heteroskedasticity). When there are violations of the model, programmers will note them and make appropriate corrections to the data (ie, typically through transformation of either the independent or dependent variables) or in the method of estimation.

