### **8.10.3. Cost Data**

Because health care costs are often skewed, estimated cost measures will be modeled using Manning and Mullahy's formulation. This method avoids potential difficulties introduced by transformation and retransformation of the dependent variable. Coefficients from a generalized linear model (GLM) are estimated cost ratios. Cost ratios, 95 percent confidence intervals, and p-values will be presented for each categorical covariate included in the model. For ease of interpretation and comparison with the bivariate results, the average cost will be predicted for each cohort and may also be predicted for pre-determined levels of other patient characteristics (eg, combination vs. monotherapy, gender).

If a significant number of patients have zero values for costs (eg, more than 5% in one of tofacitinb+MTX patients who withdraw MTX or continue MTX groups), estimated cost measures will be compared using Blough et al.'s formulation of the traditional two-part model (ie, one equation estimating the probability of any cost and a GLM with a gamma distribution and log link estimating the level of cost). This method avoids potential difficulties introduced by transformation and retransformation of the dependent variable.

Odds ratios, 95 percent confidence intervals, and p-values will be presented for each categorical covariate included in the logistic model estimating the probability of non-zero costs, if any. Cost ratios, 95 percent confidence intervals, and p-values will be presented for each categorical covariate included in the GLM model estimating the level on costs. For continuous covariables of both models, estimates and their 95 percent confidence intervals, and p-values will be presented.

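### Section 8.10 stratifies every objective by monotherapy versus combination, a contrast the plan never defines and one that does not fit a population in which every patient starts on combination

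*Combined protocol and SAP*

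**What the plan says.** The final item of Section 8.10 before 8.10.1 sets the strata. It begins "All objectives will be evaluated for Commercial and Medicare Supplemental lives separately" and continues "as well as by Monotherapy vs. Combination regimens as identified in" Section 8.10.2, then adds prior biologic experience in four levels (0, 1, 2, 3+). The wording is not conditional.

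Section 8.10.2, the place cited for the definition, deals with confounder control ("select objectives will be conducted utilizing multivariable methods as described above"), choice of outcomes, choice of predictors and regression diagnostics. Neither regimen is mentioned there.

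Section 8.2.1, criterion 1c, governs entry: "Patients must have an initial prescription for oral MTX in the period between 30 days prior to index date and 30 days following index date". A second MTX fill must follow, summarised as "at least two claims/administrations with no 60 day gap".

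Section 8.3 forms the exposure cohorts from MTX gaps of more than 60 days in the 12 months after index: discontinued, interrupted and persistent.

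Section 8.4 names three subsets for the analysis of select outcomes: insurance type, number of prior biologics, and pre-index MTX, the last described only as "Treatment with MTX prior to index medication".

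Section 8.10.3 says costs may also be predicted at levels of other patient characteristics, with the example "eg, combination vs. monotherapy, gender".

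**The concern.** A stratifier that applies to every objective has to be defined, has to vary among the patients studied, and has to be something other than the exposure. This one has no definition where the plan says it will be found, and the two natural ways of supplying one both fail. Section 8.11 has the analyses programmed from the protocol, and Annex 1 lists no stand-alone document that could fill the gap. A programmer would have to invent a rule, possibly after seeing the data, and tables built on a post-index rule would look like subgroup results while partly re-describing the cohorts.

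The list of strata also differs from the plan's own list of subsets. Prior MTX use bears directly on a study of MTX withdrawal, yet its place among the Section 8.10 strata is taken by the contrast that cannot be used.

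**Working it through.** No figure is stated for this point and none is needed. The check sets the sections side by side.

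**1. Scope.** Section 7 lists one primary and five secondary objectives. The Section 8.10 sentence covers all of them, 1 + 5 = 6.

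**2. Cross-reference.** Section 8.10.2 contains no definition of the regimens. Sections 8.3, 8.4 and 8.6 define no such variable either.

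**3. Reading A: regimen at initiation.** Criterion 1c requires an oral MTX fill between day −30 and day +30 and a second fill without a 60-day gap. Every eligible patient is therefore a combination initiator as the protocol uses the term: combination 100%, monotherapy 0%. The comparison cannot be made.

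**4. Reading B: regimen after index.** Take monotherapy to mean that MTX has lapsed by the plan's own rule (gap over 60 days), and take the discontinued cohort to be those with no later fill.

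| Section 8.3 cohort | MTX gap over 60 days? | Could be classed as monotherapy? |
|---|---|---|
| Persistent | No, by definition | No |
| Discontinued | Yes | Yes, unless another NB-DMARD counts as combination |
| Interrupted | Yes, then refills | For part of follow-up |

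The monotherapy stratum then contains no persistent patients, so the comparison with the persistent cohort cannot be estimated inside it. If only MTX counts towards combination, the combination stratum has no discontinued patients either. If other NB-DMARDs count, it has only those discontinued patients who take one. Under each variant the strata are formed after index from the behaviour that defines the exposure.

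**5. Subsets against strata.**

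| Section 8.4 subset | In the Section 8.10 strata? |
|---|---|
| Commercial or Medicare Supplemental | Yes |
| Number of prior biologics | Yes |
| Pre-index MTX | No; monotherapy versus combination appears instead |

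Two of three carry over. Nothing in Section 8.10 names an outcome to be analysed by pre-index MTX.

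**6. Is the Section 8.4 subset usable as it stands?** Not yet, for two reasons.
- It has no look-back window. A patient who first fills MTX on, say, day −10 as the qualifying prescription would also count as having MTX before index. New starters and established users would be mixed. Counting only claims more than 30 days before index, within the 12-month baseline, removes the overlap, because the qualifying window opens at day −30.
- Criterion 1c speaks of an initial prescription. If that means new to MTX, established users are excluded and the subset is itself close to empty on one side. If it means the first fill within the window, they are admitted. Section 8.4 (which defines the subset) and Section 8.6.2 (which lists methotrexate among pre-index NB-DMARDs) suggest the second meaning, but the plan does not say so.

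**The case against.** Five points can be made on the other side.

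- **Pre-index MTX is not abandoned.** A reader might infer from the Section 8.10 list that it is never analysed. The documents do not support that. Section 8.4 commits the subset to select outcomes, Section 8.6.2 makes pre-index methotrexate a baseline indicator, Section 8.10.1 describes all study variables, and Section 8.10.2 makes it a candidate covariate. What stands is narrower: it is missing from the strata and has no named outcome.
- **Some patients may be on tofacitinib alone on the index day.** Criterion 1c allows the first MTX fill up to 30 days after index. This is correct, so the 0% applies to initiation regimen over the protocol's window and not to drug supply on day 0. A split on index-day supply would separate patients by fill timing, and the plan proposes no such split.
- **Overlap with the discontinued cohort may be far from complete.** A reader might infer that monotherapy after index and MTX discontinued are the same group. That cannot be shown. Section 6 describes combination use with MTX or other NB-DMARDs, Section 8.6.3 tracks their addition, and interrupted patients fit neither class cleanly. The overlap should be called large but unquantified. The empty persistent cell in step 4 does not depend on its size.
- **The Section 8.10.3 predictions are optional.** The text says costs may be predicted and gives the contrast only as an example, so no required output fails there. This stands; the example should go for consistency.
- **Nothing else breaks.** Deleting the phrase leaves the cohort comparisons, the models and the other two strata intact. This also stands, and it limits the weight of the point.

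**Conclusion.** The point holds. A stratification required for all six objectives has no definition at the place cited. By initiation regimen it is empty (0% monotherapy). Built from post-index MTX use, it largely restates the exposure cohorts, and the monotherapy stratum has no persistent patients for comparison. Separately, pre-index MTX is defined as a subset but is not among the Section 8.10 strata and has no outcome assigned.

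The conclusion assumes that initiation regimen is judged over the window in criterion 1c and that lapse of MTX follows the 60-day rule in Section 8.3. A different post-index rule could fill more cells, but the plan states none, and any such rule would still be formed after index.

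The effect is confined to these stratified outputs. The main cohort comparisons, the cost and effectiveness models, and the insurance and prior-biologic strata do not depend on it. It should be corrected before programming.

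**What to change.** 1. In Section 8.10, delete the monotherapy versus combination stratum. In Section 8.10.3, delete the matching example.
2. In its place, list the pre-index MTX subset of Section 8.4 and name the outcomes to be analysed by it.
3. Give that subset a look-back that excludes the qualifying fill, for example any MTX claim more than 30 days before index within the 12-month baseline.
4. State in criterion 1c whether the initial prescription may come from an established MTX user. If not, delete the stratum without a substitute.
5. Label any cohort-by-subset interaction exploratory. Section 8.10.6 expects a relatively small sample, and Section 8.8 reports no sample size computation.

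The cost is wording in four sections (8.2.1, 8.4, 8.10 and 8.10.3) and one subgroup run in place of another. It uses data the study already holds.

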#### **8.10.1. Descriptive Analysis**

All study variables, including pre- and post-index measures, will initially be analyzed descriptively. In general, numbers and percents will be provided for dichotomous and polytomous variables, while means, medians, and standard deviations will be provided for continuous variables. Missing or unavailable data will not be imputed.

Results will be stratified by treatment cohort, bivariate comparisons of pre- and post-index measures will be provided, and appropriate tests (eg, t-test, Mann Whitney-U test, chi-square test) will be used based on the distribution of the measure. The analysis that is performed (ie, the methods that are used and the patients who are included) will be specific the objective being examined. Descriptive techniques will be implemented for each objective.

Multivariable techniques (including effect decomposition) will be used when comparing outcomes and controlling for differences in patient characteristics between study cohorts.

#### **8.10.2. Multivariate Analysis**

To control for possible confounding of the relationship between the outcomes and independent variable of interest, select objectives will be conducted utilizing multivariable methods as described above.

Final outcomes for multivariate analysis will be selected after review of descriptive results. Possible outcomes of interest include: total all-cause health care cost, total RA-related health care cost, cost of biologics/tofacitinib/administration/nb-DMARDs, medication effectiveness (yes vs. no).

For each model, specific predictors to be included will be determined based upon clinical rationale and statistical significance. Variables listed in [Section 8.6.1](#) and [8.6.2](#) will be considered for inclusion in the multivariable models. Additional variables identified throughout the course of the study will also be considered. Following standard procedure,

regression diagnostics will be performed for each model to assess goodness of fit and violations of model assumptions (eg, multicollinearity, heteroskedasticity). When there are violations of the model, programmers will note them and make appropriate corrections to the data (ie, typically through transformation of either the independent or dependent variables) or in the method of estimation.

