### **8.12. Limitations of the Research Methods**

#### **8.12.1. Claims**

Limitations that are general to claims database analyses and specific to this study should be noted. First, diagnosis of autoimmune conditions will be identified using ICD-10-CM diagnosis codes, which are subject to potential miscoding. Second, the baseline period for this study will be 12 months long. Therefore, patients treated with a biologic in the baseline can be considered to be continuing users of biologic therapy; however, patients with no biologic use in the baseline may have just been off therapy for the 12 months prior. Lastly, this study will include an examination of medication effectiveness at 1 year among all biologic users. Effectiveness will be measured using a validated algorithm; however, the algorithm was not validated for all medications being included. Specifically, tofacitinib was approved for treatment of RA after the algorithm was developed. This study will include consultation with physicians to determine if the algorithm is valid for all study medications or if modifications need to be implemented.

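### Section 8.10.2 leaves the choice of outcomes for adjusted analysis until the cohort contrasts have been seen, gives no criterion, and conflicts with the commitments made under the secondary objectives in Section 8.10

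*Combined protocol and SAP*

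**What the plan says.** Section 8.10.2 sets the rule: "Final outcomes for multivariate analysis will be selected after review of descriptive results". It then names four candidates without closing the list: "Possible outcomes of interest include: total all-cause health care cost, total RA-related health care cost, cost of biologics/tofacitinib/administration/nb-DMARDs, medication effectiveness (yes vs. no"). It gives no criterion for choosing among them.

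Section 8.10.1 shows what will be in view when the choice is made. The order of work is "All study variables, including pre- and post-index measures, will initially be analyzed descriptively", and "Results will be stratified by treatment cohort, bivariate comparisons of pre- and post-index measures will be provided", with t-tests, Mann-Whitney tests or chi-square tests as suits the measure.

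The secondary objectives in Section 8.10 read differently:

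- RA-related cost: "Multivariable analysis of cost will also be conducted using generalized linear models".
- All-cause cost: "Multivariable analysis of follow-up health care cost will also be conducted using generalized linear models".
- Medication effectiveness: the paragraph first says that descriptive and multivariable analysis are both to be used, then says "Analysis of this objective may also include multivariable analysis (eg, logistic regression"). Section 8.10.4 gives being effectively treated at one year as its example of an outcome to be modelled by logistic regression.

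Sections 8.10.3 and 8.10.4 call for 95% intervals and p-values from these models. The plan states no significance level, no multiplicity rule and no allowance for selection.

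**The concern.** The cohorts are formed by what happened to MTX after initiation, not by randomisation, and Section 8.10.6 expects them to differ noticeably. Readers will therefore rely on the adjusted results. Which adjusted results exist should not depend on what the crude contrasts showed.

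Crude and adjusted statistics for the same outcome come from the same patients and will usually be correlated. If an outcome is modelled because its crude contrast stands out, its adjusted p-value and interval no longer have their nominal properties, and a reader cannot tell that from the report. The plan permits this for any outcome without a firm commitment elsewhere. For the two cost totals, a programmer cannot tell whether Section 8.10 or Section 8.10.2 governs.

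**Working it through.** **Step 1. Which outcomes are open.**

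| Outcome named in 8.10.2 | Wording elsewhere | Status |
|---|---|---|
| Total RA-related cost | Section 8.10: GLM will be done | Committed, but only a possibility in 8.10.2 |
| Total all-cause cost | Section 8.10: GLM will be done | Committed, but only a possibility in 8.10.2 |
| Effectiveness at one year | Section 8.10: firm, then optional; 8.10.4: modelled | Mixed |
| Biologics/tofacitinib/administration/NB-DMARD cost | No commitment of its own | Open |
| Anything unlisted | None | Open |

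**Step 2. What selection could do.** The plan has no figure to reproduce: it gives no sample size calculation, alpha, effect size or selection rule. Everything below is assumed, for illustration:

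- Two-sided 0.05 and a single two-group contrast per outcome.
- Z₁ is the crude statistic and Z₂ the adjusted statistic, bivariate normal with correlation ρ.
- There is no true adjusted effect, so Z₂ has mean 0. Z₁ has mean δ, where δ = 0 means no crude difference and δ > 0 means a crude difference due to confounding alone.

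*Rule A: model an outcome only if crude p<0.05.* The error among modelled outcomes is

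P(|Z₂|>1.96 given |Z₁|>1.96) = P(both exceed 1.96) / P(|Z₁|>1.96).

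At δ = 0 the denominator is 0.05. For ρ = 0.7 the numerator is 0.0165, and 0.0165/0.05 is about 0.33. The other entries follow in the same way:

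| δ | ρ = 0.7 | ρ = 0.8 | ρ = 0.9 |
|---|---|---|---|
| 0 | 0.331 | 0.439 | 0.593 |
| 1 | 0.126 | 0.143 | 0.154 |
| 2 | 0.049 | 0.049 | 0.049 |
| 3 | 0.036 | 0.032 | 0.030 |

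Coverage of the nominal 95% interval among modelled outcomes is one minus these values. At δ = 0 that is about 0.67, 0.56 and 0.41.

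*Rule B: model the one outcome with the smallest crude p among k candidates, δ = 0.* By simulation with 1,000,000 draws:

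| Candidates | Correlation between outcomes | ρ = 0.5 | ρ = 0.7 | ρ = 0.9 | ρ = 0.95 |
|---|---|---|---|---|---|
| 2 | 0 | 0.068 | 0.082 | 0.094 | 0.097 |
| 2 | 0.5 | 0.065 | 0.077 | 0.087 | 0.089 |
| 4 | 0 | 0.091 | 0.127 | 0.168 | 0.177 |
| 4 | 0.5 | 0.083 | 0.112 | 0.143 | 0.150 |

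The two-candidate rows fit the plan better, since two of the four named outcomes are committed in Section 8.10.

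*Rule C: selection unrelated to the observed differences, or a list fixed in advance.* The error stays at 0.05 for each test.

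**The case against.** The strongest reply is that the plan nowhere says outcomes are picked by the size or significance of a cohort difference. The uses of descriptive data that it does state are neutral: choosing a test by the measure's distribution (8.10.1), and moving to a two-part model when more than, for example, 5% in a cohort have zero cost (8.10.3). This stands. A reader might infer from Section 8.10.2 that the adjusted p-values will be conditioned on a chance-favoured crude difference. The documents support only that they may be.

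A reader might also infer that every adjusted outcome is to be picked late. Section 8.10 rules that out for the two cost totals and partly for effectiveness. What remains is narrower, but the conflict between the sections is itself a defect.

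The 33–59% range is also a severe case. It needs a p<0.05 gate and no crude difference, while Section 8.10.6 expects noticeably different populations; the table shows inflation fading as δ grows. In addition, under that gate few null outcomes would be modelled at all. The chance that a given null outcome yields a reported significant adjusted result is 0.05 × 0.331 = 1.7% to 0.05 × 0.593 = 3.0%, and the descriptive results for the rest would still be shown. Both remarks are right about frequency. Neither restores the stated error or coverage of the models that do get reported.

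Finally, Section 8.12.1 plans physician consultation to "determine if the algorithm is valid for all study medications or if modifications need to be implemented". A reader might see a second route to result-driven choice here. The text raises a validity question, because tofacitinib was approved after the algorithm was developed, and it does not place the decision after the cohort results. Its silence on timing justifies a precaution, not a finding.

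**Conclusion.** The point holds in limited form. Section 8.10.2 defers the choice of modelled outcomes until tested cohort contrasts are available, states no criterion, and contradicts Section 8.10 on the two cost totals. The treatment-cost component, any unlisted outcome and, through its mixed wording, medication effectiveness are exposed to selective reporting of adjusted results.

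No single figure for the distortion can be defended. With no true crude difference it runs from about 7–10% (best of two) to 33–59% (p<0.05 gate, ρ 0.7–0.9), against a nominal 5%. It is about 13–15% under that gate at δ = 1 and about 5% or less at δ = 2 to 3, and 5% if selection ignores the differences. Alpha, ρ, δ and the selection rules are all assumptions.

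The outcomes concerned serve secondary objectives. The primary objective, treatment patterns, is to be summarised across cohorts and is not among the outcomes named for modelling. This should be changed, but it does not undermine the study.

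**What to change.** Replace the selection sentence in Section 8.10.2 with a fixed list: total all-cause cost, total RA-related cost, biologics/tofacitinib/administration/NB-DMARD cost, and effectiveness at one year. State that the adjusted model for each will be fitted and reported whatever the descriptive result, and that any outcome added later will be labelled post hoc. Bring the secondary-objective text in Section 8.10 into line, removing the optional wording for effectiveness and adding the treatment-cost component.

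As a secondary precaution only, settle any change to the effectiveness algorithm before outcomes are tabulated by cohort.

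The cost is protocol wording, since these models are already anticipated. The sponsor loses the freedom to skip a model. Fixing the list removes the selection problem but not multiplicity: with four independent tests at 0.05 the chance of at least one false positive is 1 − 0.95⁴ = 0.1855 (0.156 by simulation at a between-outcome correlation of 0.5). The report should present the four results together.
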